All participants randomized in the study (intention-to-treat population) will be included in the primary endpoint analysis. Should a participant withdraw from the study before the 1-hour NRS pain assessment, the NRS value used in the analysis will be the last value carried forward. In addition, we will conduct a sensitivity analysis that includes only participants with a 1-hour post randomization NRS pain rating (per-protocol population). Study dropout rates will be reported by treatment arm.

The mean change in pain intensity from treatment *initiation* until one hour after treatment initiation will be compared between the two arms. Non-inferiority will be evaluated by testing whether the lower bound of the 90% CI for difference in pain change scores is greater than -0.9, the margin of equivalence. Specifically, the mean change in NRS pain scores (assessed on an 11-point Likert scale with 0 = no pain and 10 = worst pain) from treatment initiation to one hour post-initiation will be calculated for both groups. The group difference in pain change scores (mean pain change in the fentanyl group minus that in the IV hydromorphone group) and the associated two-sided 95% CI for the difference will be estimated. Non-inferiority of nasal fentanyl over IV hydromorphone will be concluded if the lower bound of the 90% CI around the estimated difference in pain score change lies above -0.9 points. This analysis will be in the intention-to-treat population but will be repeated in the per protocol population for sensitivity analysis. Both sets of results will be considered for evaluating the study objective.

The secondary efficacy endpoint is the change in NRS pain scores from randomization to one hour after randomization, which will be summarized using mean, standard deviation, minimum, median and maximum values. A two-sample t-test will be used to assess group difference in pain score change. In addition, analysis of covariance will be used to determine whether significant differences exist between the nasal fentanyl and IV hydromorphone groups in pain intensity scores at one hour post randomization with treatment group (fentanyl vs. IV hydromorphone) and baseline pain intensity included as independent variables. Models will be constructed to adjust for relevant baseline demographic and clinical factors, such as age, treatment dose, and disease type. Additional exploratory analyses will include time to maximal pain relief as well as summed pain intensity ratings for the entire observation period calculated as the sum of time-weighted pain intensity scores. Group differences in the summed pain intensity will be assessed using the area under the curve derived using the trapezoidal rule (Cappelleri et al., 2009).

Because study treatments are FDA approved for treatment of breakthrough pain in cancer patients, no formal safety monitoring rule will be established; however, all side effects and adverse events will be monitored continuously by the principle investigator. To address the secondary objective #2, the safety analysis will include data summaries of treatment side effects and adverse events by study group. Side effects will be tallied and reported by number and percent for the worst reported severity. Laboratory values and clinical measures will be summarized by treatment group using simple descriptive statistics, such as mean change from baseline value to the 4 hours after treatment initiation or end of treatment, whichever occurs first. In addition, any delayed side effects that occur during the first 24 hours will be reported. This randomized trial will be monitored by the MD Anderson Data Safety Monitoring Board.

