Fentanyl is a pure opioid agonist whose principal therapeutic action is analgesia. Other members of the class known as opioid agonists include substances such as morphine, oxycodone, hydromorphone, codeine, and hydrocodone.

Pharmacokinetics

Absorption:

In a study that compared the relative bioavailability of Lazanda and an oral transmucosal fentanyl citrate product, the bioavailability of fentanyl from Lazanda was approximately 20% higher. Fentanyl is absorbed from the nasal mucosa following intranasal administration of Lazanda, with median Tmax values ranging from 15-21 min after administration of a single dose. Cmax and AUC values for fentanyl following administration of Lazanda increase linearly over the 100- to 800-mcg dose range.

Distribution:

Fentanyl is highly lipophilic. The plasma protein binding of fentanyl is 80% to 85%. The main binding protein is alpha-1-acid glycoprotein, but both albumin and lipoproteins contribute to some extent. The mean volume of distribution at steady state (Vss) was 4 L/kg.

Metabolism:

The metabolic pathways following intranasal administration of Lazanda have not been characterized in clinical studies. The progressive decline of fentanyl plasma concentrations results from the uptake of fentanyl in the tissues and biotransformation in the liver. Fentanyl is metabolized in the liver and in the intestinal mucosa to norfentanyl by cytochrome P450 3A4 isoform. In animal studies, norfentanyl was not found to be pharmacologically active.

Elimination:

The disposition of fentanyl following intranasal administration of Lazanda has not been characterized in a mass balance study. Fentanyl is primarily (more than 90%) eliminated by biotransformation to N-dealkylated and hydroxylated inactive metabolites. Less than 7% of the administered dose is excreted unchanged in the urine, and only about 1% is excreted unchanged in the feces. The metabolites are mainly excreted in the urine, while fecal excretion is less important. The total plasma clearance of fentanyl following intravenous administration is approximately 42 L/h.

Adverse Reactions

Clinical Studies Experience

Because clinical trials are conducted under widely varying conditions, adverse event rates observed in the clinical trials of a drug product cannot be directly compared to rates in the

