The following baseline evaluations will be performed on consented subjects prior to study drug administration: vital signs, oxygen saturation, Ramsay Sedation Scale (Table 2) (Ramsay, 197). The baseline pain intensity will be rated using NRS, and a blood sample will be drawn for standard of care laboratory investigation of the cause of pain or exacerbation of pain.

Intervention:

Intervention Arm: A Lazanda dose [100 mcg] at time 0 (defined as the time when intranasal Lazanda spray is administered) with a rescue dose allowed at time 0.5 hour (h).

Control Arm: An equipotent opioid dose [hydromorphone 1.5 mg pushed intravenously (IV)] at time 0 (defined as the time of completion of opioid IV push) with a rescue dose allowed at time 0.5 hour (h).

For subjects with pain NRS > 4 who desire additional analgesics at thirty minutes after Time 0 (i.e., Time 30 minutes), a second dose of medication will be administered as in the table above. Subjects with excessive sedation (Ramsay Sedation Scale < 4) will not receive analgesics at Time 30 minutes.

After another 90 minutes (i.e., Time 120 minutes), for patients with unrelieved pain (NRS >6 and Ramsay Sedation Scale <4), the patient may receive supplemental IV bolus doses of opioid as clinically indicated and ordered by the treating physician.

Table 2. **Ramsey Sedation Scale**

Wakeful State	Scale	Description
If Awake	Ramsay 1	Anxious, agitated, restless
	Ramsay 2	Cooperative, oriented, tranquil
	Ramsay 3	Responsive to commands only
If Asleep	Ramsay 4	Brisk response to light glabellar tap or loud auditory stimulus
	Ramsay 5	Sluggish response to light glabellar tap or loud auditory stimulus
	Ramsay 6	No response to light glabellar tap or loud auditory stimulus

10 Evaluation during Study

We will perform measurements described in this section for 4 hours after initiation of the drug intervention while the patient is in the ED. The average length of stay for patients presenting with severe pain to our ED is currently 9 hours.

Pain Measurements: Pain measurement by NRS will be obtained at the time of randomization, time of treatment initiation, and every 15 min from administration of the first dose of pain medication up to Time 120 min and then every 30 min from Time 120 min to Time 240 min. At 60 min after randomization, one additional NRS rating will be obtained.

Primary Outcome Measure:

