from the hospital or by patient visit if the patient is hospitalized, within 24 hours after study completion.

Intranasal fentanyl is generally well tolerated with the most common side effects consisting of nausea, vomiting, headache, and sedation (side effects common to all opioids).

Unexpected Adverse Drug Event

All external adverse events/safety reports received from the sponsor will be submitted to the IRB through the Office of Protocol Research as described for the “External Adverse Event Report” located under section 1 of the OPR Forms Manual.

Adherence to MDA Policy and Procedure for Reporting of Serious Adverse Events.

This study will follow the MDA policy and procedures for reporting of adverse and serious adverse events. All adverse events and serious adverse events will be documented and available for review if desired. Criteria for reporting of events before routine review will be determined based on established institutional guidelines.

12 Criteria for Evaluation and Endpoint Determination

Measurements

NRS measures will be obtained at triage, randomization, time 0 (initiation of drug intervention) and every 15 minutes for 120 minutes and then every 30 minutes from time 2 to 4 hours, and at 60 min after randomization.

Vital signs, oxygen saturation and respiratory rate will be recorded at each time point of NRS measurement.

Adverse reactions of nausea and vomiting and neuropsychiatric adverse effects will be monitored.

Sedation will be measured by Richmond Agitation Sedation Scale (RASS) (Table 3) at Time 1 h (i.e., one hour after initiation of drug delivery). RASS is a scale used to grade the sedation or agitation level of a patient in a clinical setting (Sessler et al., 2002).

Table 3: Richmond Agitation Sedation Scale

Points	Classification	Description
4	Combative	Overtly combative or violent; immediate danger to staff
3	Very agitated	Pulls on or removes tube(s) or catheter(s) or has aggressive behavior toward staff
2	Agitated	Frequent nonpurposeful movement or patient–ventilator dyssynchrony
1	Restless	Anxious or apprehensive but movements not aggressive or vigorous
0	Alert and calm	
-1	Drowsy	Not fully alert, but has sustained (more than 10 seconds) awakening, with eye contact, to voice

-2	Light sedation	Briefly (less than 10 seconds) awakens with eye contact to voice
-3	Moderate sedation	Any movement (but no eye contact) to voice
-4	Deep sedation	No response to voice, but any movement to physical stimulation

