All data from this study will be entered into a secured (password protected) database. Hard copy records of the consent and copies of the survey instruments will be stored securely and maintained by the study staff. Patient identifiers will be handled in a HIPAA-compliant manner. Confidentiality will be protected by identifying all medical information by the study with patient accession numbers, rather than storage by patient name or medical record number.

14 Criteria for Removal from Study

Since only one dose of Lazanda with one rescue dose in 30 min will be administered, patients with adverse reactions or side effects will not be removed from the study. The adverse reactions or side effects will be managed medically according to standard care.

15 Statistical Considerations

Sample Size Calculations

This is a two-arm study enrolling 84 cancer patients who present to the emergency department with severe pain (NRS pain score ≥ 7). Consented participants will be equally randomized to receive fentanyl nasal spray or IV hydromorphone for pain treatment. MD Anderson's Clinical Oncology Research System (CORE) will be used to register participants and randomize participants to the study treatment arms.

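### The only vital-sign summary the plan names is a mean change to one loosely defined end time, which cannot show isolated falls in oxygen saturation or respiratory rate

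*Combined protocol and SAP*

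**What the plan says.** The safety paragraph of Section 15 (Statistical Analysis) says that laboratory values and clinical measures will be "summarized by treatment group using simple descriptive statistics, such as mean change from baseline value". In full, the example is "mean change from baseline value to the 4 hours after treatment initiation or end of treatment, whichever occurs first". The second of these two end points is not defined anywhere.

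Other sections bear on what it could mean:

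- **Dosing.** Section 14 reasons: "Since only one dose of Lazanda with one rescue dose in 30 min will be administered". In Section 7 the second dose is conditional, being offered "For subjects with pain NRS > 4 who desire additional analgesics at thirty minutes after Time 0". From 120 minutes, for unrelieved pain, "the patient may receive supplemental IV bolus doses of opioid as clinically indicated and ordered by the treating physician".
- **Observation.** Section 10 states: "We will perform measurements described in this section for 4 hours after initiation of the drug intervention", while the patient is in the ED.
- **Readings.** Section 12 states: "Vital signs, oxygen saturation and respiratory rate will be recorded at each time point of NRS measurement". That is every 15 minutes to 120 minutes, then every 30 minutes to 240 minutes.
- **Drug timing.** Section 4 gives, for the nasal spray, "median Tmax values ranging from 15-21 min after administration of a single dose".

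Section 10 says that blood pressure, heart rate, oxygen saturation and respiratory rate will be watched for abnormal values. No limits are given, and no table of patients beyond a limit is planned. Section 15 does plan summaries of side effects and adverse events by arm, counts and percentages of side effects at worst severity, and reporting of delayed side effects to 24 hours.

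**The concern.** Safety is secondary objective 2 of a comparison between two opioids. The plan sets no formal safety monitoring rule and relies on continuous review by the principal investigator and on the DSMB. The final tables therefore carry much of the safety comparison, and the named statistic has two weaknesses.

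First, the end time is ambiguous. One available meaning places it before most post-dose readings. It would then also depend on whether the patient took the rescue dose, which happens after randomisation, so the arms could be summarised over different periods.

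Second, whatever the end time, a mean change to one point answers the wrong question. The harm of interest with an opioid is a marked fall in a few patients, probably brief and early. A mean at one late time can look flat in both arms while such falls differ between them.

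**Working it through.** The plan gives no figure for this summary to reproduce, so the check counts readings and measures dilution.

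**1. Scheduled post-dose readings (Sections 10 and 12).**
15, 30, 45, 60, 75, 90, 105 and 120 minutes = 8; 150, 180, 210 and 240 minutes = 4. Total 8 + 4 = 12.

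**2. Readings inside the window, by meaning of end of treatment.**

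| Meaning | End time | Inside | Outside |
|---|---|---|---|
| Last study dose, no rescue | 0 min | 0 of 12 | 12 (100%) |
| Last study dose, with rescue | 30 min | 2 of 12 | 10 (83%) |
| Supplemental IV opioid, if given at 120 min | 120 min | 8 of 12 | 4 (33%) |
| End of the 4-hour period | 240 min | 12 of 12 | 0 |

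**3. Readings actually used.** A change from baseline to an end time uses one post-dose reading at most. Even with the end at 240 minutes, 12 - 1 = 11 of the 12 readings do not enter the statistic.

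**4. Position relative to exposure.** With a median Tmax of 15 to 21 minutes after the first dose, the readings nearest the fentanyl peak are those at 15 and 30 minutes. If the rescue dose is absorbed on the same timescale (an assumption), its peak falls at 30 + 15 = 45 to 30 + 21 = 51 minutes. A 4-hour value is far from both, and may follow physician-ordered opioid given from 120 minutes. An end time of 0 minutes precedes the first peak, and one of 30 minutes precedes the rescue peak.

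**5. Dilution by the mean.** Shift in arm mean = (patients affected × individual change) / 42, with 42 per arm from Section 15. The individual falls below are assumed; the documents give none.

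- One patient, oxygen saturation down 10 points: 1 × 10 / 42 = 0.24 points.
- One patient, down 20 points: 1 × 20 / 42 = 0.48 points.
- Three patients, down 10 points each: 3 × 10 / 42 = 0.71 points.
- One patient, respiratory rate down 6 to 10 per minute: 6/42 to 10/42 = 0.14 to 0.24 per minute.

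These shifts also require the fall to be present at the end time. A fall that has recovered by then contributes nothing.

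**6. The same data by patient.** Three affected patients are 3/42 = 7.1% (exact 95% CI 1.5% to 19.5%); one is 1/42 = 2.4%. Even 0/42 is informative, with an exact upper limit of 8.4% (two-sided 95%).

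**The case against.** A reader might infer that the plan throws away most of its safety readings. The documents do not support that as a statement of fact. It needs end of treatment to mean the last study dose, and then the 4-hour limb could never apply. In patients without rescue, the change would also stop before any post-dose reading. The authors are unlikely to have meant this. Measurement runs for 4 hours while the patient is in the ED, and some early withdrawal (5% at most) is expected, so 4 hours or earlier departure is the more natural sense. The rule also limits a summary, not data collection, which continues to 240 minutes.

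A reader might also infer that respiratory depression would be hidden altogether. That goes too far. The mean is offered as an example, so other statistics are not excluded. Respiratory depression recorded as an adverse event would be counted by arm, and recorded side effects are tabulated at worst severity. The principal investigator and the DSMB watch the trial as well.

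The Tmax argument has limits too. The figure is a single-dose plasma median for the nasal spray. The documents give no repeat-dose value, nothing for hydromorphone, and no timing of respiratory effect.

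All of this stands, and it narrows the point without removing it. Wording that permits other statistics commits to none. Adverse events are gathered spontaneously and by nondirected questioning (Section 12), so a fall in saturation without symptoms may never become an event. The SERSDA list has no respiratory item and is scored once, at 4 hours; RASS is taken once, at 1 hour. The trial is open label, so event reporting may differ by arm. The measured values are the more objective record, yet no patient-level table is planned for them.

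**Conclusion.** The point holds as a moderate reporting gap in a secondary objective. The loss of 10 to 12 of 12 readings is conditional on one meaning of an undefined term; on the more natural meaning few or none are lost. What holds on every reading is that the one named summary uses a single end time, ignores the intermediate readings and cannot show isolated abnormal values. On the assumed falls, one to three affected patients of 42 move an arm mean by 0.24 to 0.71 saturation points, while a patient-level table would show them as 2.4% to 7.1%. The gap concerns abnormal measurements that are not reported as events. It does not touch the primary non-inferiority analysis, and nothing is lost irretrievably, because the readings are taken in any case.

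**What to change.** In the safety paragraph of Section 15:

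1. Replace the end-of-treatment clause with the 0 to 240 minute observation period, or the last available reading if the patient leaves early. This step alone is not enough, because a change to one end time would still leave the intermediate readings unused.
2. Report by arm the distribution of each patient's worst post-dose oxygen saturation, respiratory rate and systolic pressure.
3. Report by arm the number and percent of patients beyond limits that the investigators prespecify, with exact 95% confidence intervals.
4. Keep mean change as an additional summary.

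The cost is a few sentences, a few tables, and agreement on the limits before the data are examined. No new data, visits or patients are needed.

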Study Type	Enrollment Site	Protocol No.	Study Chair	Disease Category	Priority	Title	Enrollment	Funded	Status
Observational	Emergency Center	2012-0122	[name]	Emergency Medicine-Pain	1	Management of Chronic Pain in the Emergency Department	223/285	Yes	Active
Observational	Emergency Center	2012-0640	[name]	Emergency Medicine-Palliative Care	2	Delirium in the ED	231/500	Yes	Active
Observational/Lab	Other	2012-0642	[name]	Emergency Medicine-Pain	1	Neuropathic Pain in Head and Neck Cancer	24/1200	Yes	Active
Observational	Other	2012-1035	[name]	Emergency Medicine-Pain	2	Pain in Survivors of Head and Neck Cancer	145/500	No	Active
Observational	Other	Lab10-0985	[name]	Emergency Medicine	3	Case-Control Study of metabolic syndrome and breast cancer in Puerto Rico	94/346	Yes	Active
Study Type	Enrollment Site	Protocol No.	Study Chair	Disease Category	Priority	Title	Enrollment	Funded	Status
Lab-Based	Emergency Center	Lab06-0616	[name]	Emergency Medicine	1	Generation of cell lines from tumor cells in bodily fluids	4/60	No	Active
Study Type	Enrollment Site	Protocol No.	Study Chair	Disease Category	Priority	Title	Enrollment	Funded	Status
Retrospective Chart Review	Other	DR09-0635	[name]/[name]	Emergency Medicine	1	Implementation of a standardized sepsis order set		No	Active
Retrospective Chart Review	Other	DR08-0066	[name]	Emergency Medicine	1	A retrospective chart review of patients with oncologic emergencies	20,000	No	Active
Retrospective Chart Review	Other	PA12-0378	[name]	Emergency Medicine	1	A retrospective chart review of the effects of metabolism in cancer	80,000	No	Active
Retrospective Chart Review	Other	PA13-0163	[name]	Emergency Medicine	1	Association between body composition and docetaxel-induced toxicity in male prostate cancer patients receiving single agent docetaxel therapy	1,200	No	Active
Retrospective Chart Review	Other	PA13-0331	[name]	Emergency Medicine	1	Emergency Departments Visits among Cancer Patients in Harris County, TX		No	Active
Retrospective Chart Review	Other	PA11-1022	[name]	Emergency Medicine	1	Evaluation of Fibroblast Growth Factors as Circulating Markers of Prognosis and Response to Therapy in Breast Cancer Patients		No	Active
Retrospective Chart Review	Other	PA13-0666	[name]	Emergency Medicine	1	Non-Coding RNA and cytokines in sepsis and cancer	249	No	Active
